3. STUDY OBJECTIVES AND ESTIMANDS

3.1. Primary Objectives and Estimands: Pharmacokinetics and Safety

Pharmacokinetic Objective(s)	
To evaluate the pharmacokinetics (PK) of brensocatic in participants with cystic fibrosis (CF) following once daily (QD) oral administration of study drug	
Population	Participants with CF defined by the inclusion and exclusion criteria of the CSP who received brensocatic
Treatment Regimen	1 tablet QD of brensocatic (actual treatment)
Endpoints	C_{max} , t_{max} , AUC_{0-24} , and $t_{1/2}$ on Day 1 and Day 28
Population Level Summary	Mean brensocatic dose levels for C_{max} , AUC_{0-24} , and $t_{1/2}$, median for t_{max}
Intercurrent Event (ICE)	
 Early discontinuation from brensocatic for any reason Not on stable cystic fibrosis transmembrane conductance regulator (CFTR) modulators for participants on modulators
Strategy	
For the first ICE, the While-On-Treatment strategy (including up to Day 35 follow-up period) will be applied.
 
For the second ICE, the Treatment Policy strategy will be used.

C_{max} = maximum plasma concentration, t_{max} = time to maximum plasma concentration, AUC_{0-24} = area under the concentration-time curve from time 0 to 24 hours post-dose, $t_{1/2}$ = elimination half-life.

Safety Objective(s)	
To evaluate the safety of brensocatic compared to placebo in participants with CF	
Population	Participants with CF defined by the inclusion and exclusion criteria of the CSP
Treatment Regimen	1 tablet QD of brensocatic or placebo (actual treatment)
Endpoints	Participant reported treatment-emergent adverse event (TEAE) and type of TEAE
Population Level Summary	Number and percentage of participants with each type of TEAEs and number of TEAEs
ICE	
 Early discontinuation from randomized investigational product (IP) for any reason
Strategy	The While-On-Treatment strategy (including the 28-days follow-up) will be applied.

3.2. Secondary Objective and Estimand: Pharmacokinetics

Pharmacokinetic Objective(s)	
To evaluate the dose-dependency of brensocatib exposure	
Population	Participants with CF defined by the inclusion and exclusion criteria of the CSP who received brensocatib
Treatment Regimen	1 tablet QD of brensocatib (actual treatment)
Endpoints	C_{max} , AUC_{0-24} , and AUC_{last} on Day 1 and Day 28
Population Level Summary	Slope from a statistical model (if data allow estimation based on a statistical model) or ratio of geometric means (GMs)
ICE	
 • Early discontinuation from brensocatib for any reason • Not on stable CFTR modulators for participants on-modulators
Strategy	
For the first ICE, the While-On-Treatment strategy (including up to Day 35 follow-up period) will be applied.
 
For the second ICE, the Treatment Policy strategy will be used.

C_{max} = maximum plasma concentration, AUC_{0-24} = area under the concentration-time curve from time 0 to 24 hours post-dose, AUC_{last} = area under the concentration-time curve from time 0 to the last timepoint with measurable concentration.

3.3. Exploratory Objectives and Estimands

Pharmacodynamic Objective(s)	
To evaluate the effect of brensocatib compared with placebo on the concentration of Neutrophil Elastase (NE), Cathepsin G (CatG), and Proteinase 3 (PR3) in sputum over the 28-day treatment period	
Population	Participants with CF defined by the inclusion and exclusion criteria of the CSP
Treatment Regimen	1 tablet QD of brensocatib or placebo (actual treatment)
Endpoints	Percentage inhibition from baseline to Day 14 and Day 28 for concentration of NE, CatG, and PR3 in sputum
Population Level Summary	Treatment means for observed values and for percent inhibition from baseline
ICE	
 • Early discontinuation from randomized IP for any reason, • Use of antibiotics during an acute event that could affect neutrophil serine protease (NSP) levels
Strategy	The While-On-Treatment strategy (including up to Day 35 follow-up period) will be applied for both ICEs.

Pharmacodynamic Objective(s)	
To evaluate the effect of brensocatib compared with placebo on the concentration of NE, CatG, and PR3 in blood over the 28-day treatment period	
Population	Participants with CF defined by the inclusion and exclusion criteria of the CSP

Treatment Regimen	1 tablet QD of brensocatib or placebo (actual treatment)
Endpoints	Percentage inhibition from baseline to Day 14 and Day 28 for concentration of NE, CatG, and PR3 in blood
Population Level Summary	Treatment means for observed values and for percent inhibition from baseline
ICE	
 • Early discontinuation from randomized IP for any reason, • Use of antibiotics during an acute event that could affect NSP levels
Strategy	The While-On-Treatment strategy (including up to Day 35 follow-up period) will be applied for both ICEs.

Efficacy Objective(s)	
To assess the effect of brensocatib compared with placebo on lung function, as measured by change in pulmonary function tests including ppFEV ₁ , FEV ₁ , FVC, and FEF _(25-75%) at Day 28	
Population	Participants with CF defined by the inclusion and exclusion criteria of the CSP
Treatment Regimen	1 tablet QD of brensocatib or placebo (randomized treatment)
Endpoints	Change from Baseline to Day 28 in prebronchodilator ppFEV ₁ , FEV ₁ , FVC, and FEF _(25-75%)
Population Level Summary	Treatment means or difference in means if data allow estimation based on a statistical model
ICE	
 • Early discontinuation from randomized IP for any reason
Strategy	The While-On-Treatment strategy will be applied.

FEV₁ = forced expiratory volume in 1 second, ppFEV₁ = percent predicted forced expiratory volume in 1 second, FVC = forced vital capacity, FEF_(25-75%) = forced expiratory flow between 25% and 75% of forced vital capacity.

Efficacy Objective(s)	
To evaluate the effect of brensocatib compared with placebo on quality of life (QoL) as measured by cystic fibrosis questionnaire (revised version) (CFQ-R) ¹ through the 4-week treatment period	
Population	Participants with CF defined by the inclusion and exclusion criteria of the CSP
Treatment Regimen	1 tablet QD of brensocatib or placebo (randomized treatment)
Endpoints	Change from Baseline to Day 14 and Day 28 for the CFQ-R Respiratory Domain score
Population Level Summary	Treatment means or difference in means if data allow estimation based on a statistical model
ICE	
 • Early discontinuation from the randomized IP for any reason
Strategy	The While-On-Treatment strategy (including up to Day 35 follow-up period) will be applied.

CFQ-R = Cystic Fibrosis Questionnaire-Revised.

Microbiology Objective(s)	
To evaluate the effect of brensocatib on sputum microbiology	
Population	Participants with CF defined by the inclusion and exclusion criteria of the CSP
Treatment Regimen	1 tablet QD of brensocatib or placebo (randomized treatment)
Endpoints	Change from Baseline to Day 28 in number of colony-forming units for microbial species
Population Level Summary	Treatment means and change from baseline
ICE	
 • Early discontinuation from randomized IP for any reason
Strategy	The While-On-Treatment strategy will be applied.

4. STUDY DESIGN

4.1. Summary of Study Design

This is a Phase 2a, single-blind, randomized, placebo-controlled, parallel-group, multiple-dose study to assess the PK, PD, and safety of brensocatib 10, 25, and 40 mg QD in participants with CF. Following review of PK and safety data by a SRC, and provided that the SRC deems it appropriate to administer the next dose, a cohort of participants will receive brensocatib 65 mg QD on the same schedule as the previous cohorts. A tablet formulation of brensocatib 65 mg is not yet available; therefore, participants assigned to the 65 mg dose cohort will receive 1 tablet of brensocatib 25 mg and 1 tablet of brensocatib 40 mg.

Overall, the study will enroll approximately 25 to 34 participants. The first three brensocatib arms (10 mg, 25 mg, and 40 mg QD) will enroll approximately 7 participants each, and the placebo arm will enroll approximately 4 participants. For the active treatment arms, there will be 2 strata: 5 participants who have previously received and will continue to receive CFTR modulators as concomitant medication (CFTR modulator stratum), and approximately 2 participants who have either never previously received CFTR modulators or have not been administered CFTR modulators within 30 days prior to Screening (Visit 1) and will not receive CFTR modulators during the study (non-modulator stratum). For the placebo arm, approximately 3 participants will be randomized into the CFTR modulator stratum and 1 participant in the non-modulator stratum.

Each dose group will enroll participants in a 5:1 ratio (active : placebo) for the CFTR modulator stratum. For the non-modulator stratum, approximately 6 participants will be randomized to receive active treatment (10 mg, 25 mg, or 40 mg brensocatib) and approximately 1 participant to placebo.

If there are no safety issues observed in the first 3 dose cohorts, a 65 mg dose cohort will be similarly randomized: 7 participants (5 participants CFTR modulator and 2 participants non-modulator stratum) in active treatment and 2 participants in placebo (1 participant each in the CFTR modulator and non-modulator strata), increasing the sample size from approximately 25 to 34 participants.

The overview below illustrates the prospective number of participants based on approximately 25 participants in the first 3 cohorts (10 mg, 25 mg, and 40 mg) and approximately 9 participants in the fourth cohort (65 mg).

Table 1: Participant Randomization Scheme by Dose Cohort and CFTR Modulator Status

CFTR Modulator Status	Active (Brensocatic)				Placebo	Total Number of Participants**
	10 mg	25 mg	40 mg	65 mg*		
CFTR Modulator	5	5	5	5	4	24
Non-Modulator	2	2	2	2	2***	10
Total Number of Participants**	7	7	7	7	6	34

CFTR = cystic fibrosis transmembrane conductance regulator.

* Participants will only be randomized to the 65 mg dose cohort if there are no safety issues observed and the PK data demonstrates a need in the first 3 dose cohorts (10 mg, 25 mg, and 40 mg).

** Approximate number of participants.

*** Overall, approximately 1 participant will be randomized to receive placebo in the non-modulator stratum from the first 3 dose cohorts (10 mg, 25 mg, and 40 mg). Pending no safety issues approximately 1 participant will be randomized in the 65 mg dose cohort to receive placebo in the non-modulator stratum.

Including the Screening (up to 28 days), Treatment (28 days), and Follow-Up Periods (28 days), the study participation duration is expected to be 84 days or less. At the end of study (EoS), all ongoing AEs will be assessed by the investigators whether they are resolved and stable or not clinically significant. Any study-related safety issues or serious events that extend past Study Day 56 (EoS) will be followed to resolution.

[figure not shown]
IP will be administered to the participant by the study center staff on Day 1 (Baseline), and at all in-clinic visits after Day 1 (Days 2, 14, and 28). On days when there is no in-clinic visit, participants will self-administer IP at home.

A SRC will review safety and PK data of completed cohorts exposed to brensocatic 10, 25, and 40 mg QD in an unblinded manner to determine whether brensocatic has an acceptable safety and PK profile and can be escalated to the 65 mg dose as planned ([Section 5.1](#)).

The purpose, function, conduct and structure of the SRC are further described in the SRC Charter.

The procedures and assessments conducted at each study visit in the study are provided in Section 1.3 of the CSP. Please refer to [Figure 1](#) for a schematic diagram of the study design.

Figure 1: Study Schema

Brensocatib dose and placebo cohorts stratified to include participants who have previously received and will continue to receive CFTR modulators as concomitant medication (CFTR modulator stratum), and participants who have either never previously received CFTR modulators or have not been administered CFTR modulators within 30 days prior to Screening (Visit 1) and will not receive CFTR modulators during the study (non-modulator stratum).

4.2. Sample Size Determination

Overall, the study will initially enroll approximately 25 participants. The 10 mg, 25 mg, and 40mg arm will enroll approximately 7 participants each, and the placebo arm will enroll approximately 4 participants. For the active treatment arms, there will be 2 strata: approximately 5 participants who have previously received and will continue to receive CFTR modulators as concomitant medication and 2 participants who have either never previously received CFTR modulators or have not been administered CFTR modulators within 30 days prior to Screening (Visit 1) and will not receive CFTR modulators during the study (non-modulator stratum). For the placebo arm, approximately 3 participants will be randomized into the CFTR modulator stratum and 1 participant into the non-modulator stratum.

If there are no safety issues observed with the first 3 doses, an additional cohort will be similarly randomized: 7 participants (5 participants CFTR modulator and 2 participants non-modulator stratum) on active treatment with 65 mg and 2 participants on placebo (1 participant each in the CFTR modulator and non-modulator strata), increasing the sample size from approximately 25 to 34 participants.

A formal sample size calculation has not been performed. The number of participants has been chosen based on feasibility, as is typical and standard for such multiple ascending dose study designs and is considered sufficient to meet the study objectives.

Brensocatic AUC_{0-24} and C_{max} will be summarized by dose group and by dose group within each stratum (CFTR modulator and non-modulator) using the GM. The precision, as measured by the width of confidence intervals (CIs), for these GMs will depend on the observed variability and sample size. The following tables present descriptions of 95% CIs for a range of possible values of the geometric coefficient of variation percentage (gCV%) of the GM. [Table 2](#) presents participants treated with brensocatic per dose group (N=10 and N=7), and [Table 3](#) presents participants treated with brensocatic per stratum (N=5) (CFTR modulator) within dose group.

Table 2: 95% CIs for Values of Inter-Participant gCV% of the AUC_{0-24} and C_{max} GM in Each Actively Treated Cohort

N	gCV%	GM 95% CI LL	GM 95% CI UL
10	30	GM÷1.234	GM×1.234
	40	GM÷1.317	GM×1.317
	50	GM÷1.402	GM×1.402
7	30	GM÷1.312	GM×1.312
	40	GM÷1.428	GM×1.428
	50	GM÷1.548	GM×1.548

Note: Assumes N=number of participants treated with brensocatic per dose group.
gCV% = geometric coefficient of variation percentage, CI = confidence interval, GM = geometric mean, LL = lower limit, UL = upper limit.

Table 3: 95% CIs for Values of Inter-Participant gCV% of the AUC_{0-24} and C_{max} GM for Each Stratum Within Each Actively Treated Cohort

gCV%	GM 95% CI LL	GM 95% CI UL
30	GM÷1.440	GM×1.440
40	GM÷1.613	GM×1.613
50	GM÷1.798	GM×1.798

Note: Assumes N=5 (number of participants treated with brensocatic per stratum in each dose group).

The range of values for gCV% is based on the results of Day 29 AUC_{last} and C_{max} in a study of patients with non-cystic fibrosis bronchiectasis (NCFBE) (INS1007-201) and on the results of Day 28 AUC_{0-24} and C_{max} in a multiple-dose study of healthy volunteers (D6190C00001).

For the primary evaluation of safety, N=10 or 7 participants per brensocatic dose group provides 80% or 68% probability, respectively, to detect an adverse event (AE) that occurs with an incidence rate of 15%, and 90% or 80% probability, respectively, to detect an AE that occurs with an incidence rate of 21%.

4.3. Randomization

After meeting all inclusion criteria and none of the exclusion criteria, participants in each stratum (CFTR modulator and non-modulator) will be randomized by an interactive web

response system (IWRS) in a 1:1:1 ratio to 1 of the first 3 dose cohorts (brensocatib 10, 25, or 40 mg); each cohort, will enroll participants in a 5:1 ratio (active : placebo) for the CFTR modulator stratum. For the non-modulator stratum, approximately 6 participants will be randomized to active treatment in the first 3 cohorts and 1 participant will be assigned placebo. If there are no safety issues in these cohorts, a 65 mg dose cohort will be similarly randomized: 7 participants (5 participants CFTR modulator and 2 participants non-modulator stratum) in active treatment and 2 participants in placebo (1 participant each in the CFTR modulator and non-modulator strata), raising the total sample size from approximately 25 to 34 participants.

This is a single-blind study: participants are blinded to the IP to which they are randomly assigned, as are the study center staff and the Investigator. The site will contact the IWRS prior to the start of IP administration for each participant. The site will record the assigned IP label number on the applicable eCRF, if the participant receives randomized treatment. Unblinding is only to occur in the case of participant emergencies and at the conclusion of the study.

Selected individuals not involved in the conduct of the study may have access to unblinded data as needed for safety review or other data review. These individuals comprise the SRC members and the Independent Clinical Pharmacologist (refer to CSP section 10.1.8).

5. PLANNED ANALYSES

5.1. Interim Analysis / Safety Review Committee Monitoring

No formal interim analysis is planned.

Safety monitoring of the study will be conducted by an SRC. There will be a first initiation meeting without review of data. A second meeting will take place after the first 3 cohorts (brensocatib 10, 25, and 40 mg QD) have completed the study (Day 56). The SRC will review available data (PK, PD, and safety data [vital signs, clinical laboratory test values, electrocardiograms (ECG), and AEs]) in an unblinded manner from all cohorts to determine if brensocatib has shown an acceptable safety and PK profile and whether the brensocatib dose should be escalated to 65 mg QD as planned. If significant safety issues arise in between scheduled meetings, ad hoc meetings will be scheduled to review those data.

The decision on whether the maximum tolerated dose (MTD) has been reached will be based on the dose limiting toxicity (DLT). The MTD is defined in this study as the highest single dose tested without incurring DLT. However, it is recognized that the MTD may differ for patients on CFTR modulators versus those not on CFTR modulators. The signs and symptoms to consider for DLT include any events that in the opinion of the SRC are relevant to brensocatib exposure, including but not limited to hyperkeratosis, severe infection, and periodontal disease. The PK profile will also be considered and compared with those of other populations (healthy volunteers and patients with NCFBE) to assess whether similar levels of exposure have been achieved with the evaluated doses.

5.2. Final Analyses

If the 65 mg QD cohort will not be conducted, the final DBL will occur after the participants in the first three cohorts have completed the study. If the 65 mg cohort will be conducted, the final DBL will occur after the participants in all four cohorts (10 mg, 25 mg, 40 mg, and 65 mg QD) have completed the study.

6. ANALYSIS SETS

6.1. Screened Analysis Set

The Screened Analysis Set comprises all participants who provide written informed consent.

Technical Note: Participants with non-missing date of informed consent will be included.

6.2. Randomized Analysis Set

The Randomized Analysis Set comprises all randomized participants. Participants will be analyzed using the treatment to which they were randomized, regardless of the treatment received.

Technical Note: Participants with a randomization number will be included.

6.3. Intent-to-Treat Analysis Set

The Intent-to-Treat (ITT) Analysis Set comprises all randomized participants who receive at least 1 dose of the IP with at least 1 pre-dose and 1 post-dose efficacy measure. Participants will be analyzed using the treatment to which they were randomized. However, per the While-On-Treatment strategy, data after participants receive a treatment that is inconsistent with their assignment will be excluded.

Technical Note: Randomized participants who received at least 1 dose of IP and have at least 1 pre-dose and 1 post-dose assessment of the same pulmonary function test or CFQ-R will be included.

6.4. Safety Analysis Set

The Safety Analysis Set comprises all randomized participants who receive at least 1 dose of IP. Participants will be analyzed using the actual treatment they received.

Technical Note: Randomized participants who received at least 1 dose of IP will be included.

6.5. Pharmacokinetic Analysis Set

The PK Analysis Set comprises all randomized participants who receive at least 1 dose of brensocatib and have sufficient data to calculate at least 1 PK parameter.

Technical Note: Randomized participants who received at least 1 dose of brensocatib (actual treatment) and for whom at least 1 PK parameter was derived will be included. Protocol deviations will be assessed on a case-by-case basis for any potential exclusion from the analysis. Participants in this analysis set will be used for all PK summaries and statistical analyses.

6.6. Pharmacodynamic Analysis Set

The PD Analysis Set comprises all randomized participants who receive at least 1 dose of IP with at least 1 pre-dose and 1 post-dose PD measure. Participants will be analyzed using the actual treatment they received.

Technical Note: Randomized participants who received at least 1 dose of IP and who have at least 1 pre-dose and 1 post-dose PD assessment of the same PD marker will be included. Participants in this analysis set will be used for all PD summaries and statistical analyses. Separate PD analysis sets for PD in blood and PD in sputum will be defined.

7. GENERAL STATISTICAL CONSIDERATIONS

7.1. General

Tables and figures will be provided by treatment group/dose level (10 mg, 25 mg, 40 mg, and 65 mg [if conducted] QD brensocatic, pooled placebo except for PK output). If sample sizes permit, summaries will be further stratified by CFTR modulator and non-modulator.

Treatment arm/dose levels will be presented in this stratified analysis if the number of observations is ≥ 2 . If the assignment to a stratum differs between the randomization file and the eCRF, the randomization file will prevail. In the listings, CFTR modulator use will be indicated by + for participants on CFTR modulator and by - for the non-modulator stratum following the Subject Identifier. For tables in the demographic and safety sections, also a Total column will be presented.

Descriptive statistics for continuous variables will be calculated at scheduled visits (nominal timepoints for PK) and will include the number of participants in the treatment group/dose level of the respective analysis set (N in column header of the table), the number of non-missing- observations (n), the number of observations below limit of quantification (BLQ) for PK and PD tests, arithmetic mean, standard deviation (SD), median, minimum, and maximum. For brensocatic plasma concentrations, the GM with 95% CI and gCV%, for PK parameters (except for t_{\max} and t_{last}), and PD tests, the GM and gCV% will be reported in addition. The GM will be derived by calculating the arithmetic mean of the natural log-transformed observations and then back-transforming the mean by exponentiation. The gCV% will be calculated as: $100 \times \sqrt{\exp[\text{variance of the log-transformed values}] - 1}$. GM and gCV% will only be calculated for quantifiable values above 0. For t_{\max} and t_{last} , only n, median, minimum, and maximum will be presented. For PK parameters, no descriptive statistics will be calculated when fewer than three individual PK parameter values are available. Summaries of continuous variables other than plasma concentrations that have some values recorded using approximate values (e.g., $<$ or $>$) will use the numeric part of the value in calculations. Rules for plasma concentrations BLQ or missing are given in [Section 11](#).

Categorical variables will be summarized by counts and by percentage of participants in the corresponding categories. The number of participants in the treatment group/dose level of the respective analysis set (N in column header of the table) and the number and percentage of non-missing observations in each category will be provided. A category including missing assessments may be added if appropriate. Footnotes will specify the base for the percentages.

Data from unscheduled visits will not be used in summaries, except for the derivation of baseline.

Listings corresponding to all summaries will be provided. Listings will also show data from unscheduled visits. Listings will be presented by treatment group/dose level, Subject Identifier, and date or visit. Listings will present the data as collected in the eCRF along with variables derived from the eCRF data.

The baseline value for safety data will be the most recent non-missing value prior to the first dose of IP.

The baseline value for efficacy data will be the most recent non-missing value prior to randomization. Note that for PFT, the most recent best effort prior to randomization will be selected.

Change from baseline at visit (i) = observed value at visit (i) – baseline value.

Percent change from baseline at visit (i) =

$$100 * [(observed\ value\ at\ visit\ (i) - baseline\ value) / baseline\ value].$$

Percent inhibition from baseline at visit (i) = $100 * [1 - \text{fold change from baseline at visit (i)}]$,
where fold change from baseline at visit (i) = observed value at visit (i) / baseline value.

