Updated the monitoring details to cover cases of suspected periodontitis/gingivitis reported during the study whereby participants should be referred to a dentist/periodontist for evaluation, diagnosis, and treatment	As an adverse event of special interest, cases of suspected periodontitis/gingivitis will be monitored and referred for evaluation	Section 8.2.7.2

Description of Change	Brief Rationale	Section Number
Clarification that the administration of a bronchodilator as part of a chronic and stable regimen is not prohibited	To clarify study procedure	Section 8.8.1
Revisions to sample size determination to account for the trial design changes, including the number of participants randomized	To align the study to the cystic fibrosis population at large with regards to the low proportion of patients (approximately only 14% of the eligible population) who are not prescribed a CFTR modulator	Section 9.2 Table 5
Updated details of exploratory endpoint analyses to include analysis by treatment group within strata (CFTR modulator and non-modulator, pooled data across all dose levels)	Proposed change due to the anticipated smaller number of participants in the CFTR non-modulator stratum	Section 9.4.1 Section 9.4.4
Clarification that no formal interim analysis is planned	To clarify study procedure	Section 9.5
Liver safety suggested actions and stopping rules updated from Hy's Law details to the Council for International Organizations of Medical Sciences (CIOMS) Drug-Induced Liver Injury (DILI) guidelines ( CIOMS, 2020 )	Updated in line with Sponsor's protocol template and agreed use of stopping rule criteria as defined in the CIOMS DILI guidelines.	Section 10.6
Summary of changes for Global Amendment 1 (dated 01 Jul 2021) moved to the Protocol Amendment History (Appendix 7)	Placement of previous protocol amendments	Section 10.7

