#### **9.4.4. Exploratory Endpoints**

NE, CatG, and PR3 (in sputum and in blood) will be exploratory endpoints. The results of these parameters will be listed by participant and timepoint and summarized by treatment group (dose levels of brensocatic and pooled placebo) and by treatment group within strata (CFTR modulator and non-modulator, pooled data across all dose levels). Where sufficient sample sizes are achieved (ie, adequate sample obtained and minimum number of quantifiable concentrations), a linear model with appropriate covariance pattern will be fit to the exploratory endpoints and between-group comparisons with associated 95% CIs will be reported.

Individual figures of NE, CatG, and PR3 versus time will be presented with all participants overlaid on the same plot for each dose level (spaghetti plots). Mean plots versus time will also be presented by treatment group (dose levels of brensocatic and pooled placebo) and by treatment group within each stratum (CFTR modulator and non-modulator).

FEV1 and CFQ-R Respiratory Domain are also exploratory endpoints. These variables will be listed and summarized in tables by brensocatic dose levels and placebo.

The relationship between dose and the 3 PD parameters (NE, CatG, and PR3) will be displayed graphically.

Additional PK-PD evaluations will be performed in separate analyses, in which the relationship between brensocatic exposure (dose or AUC) and clinical measurements (PD biomarkers, ppFEV1 and AESI) will be explored. The results from these PK-PD analyses will be reported separately.

Microbial species and colony forming units from sputum assessments will be listed and summarized by brensocatic dose levels and placebo.

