12. PHARMACODYNAMICS

For the general layout of the tables see [Section 7.1](#).

PD Tests NE, CatG, and PR3 will be assessed in blood and in sputum. Baseline is defined in [Section 7.1](#). The most recent non-missing value before the first dose of IP will be used as baseline which is either the assessment at Day 1 pre-dose or if this is not available the assessment at Screening. If both assessments are not available, the participant will not be included in the PD analysis set.

The strategies for the ICEs as outlined in [Section 3.3](#) and [Section 7.2](#) will be applied.

Descriptive statistics (including GM and gCV% for observed values and number of values BLQ) will be provided for observed values and %inhibition from baseline by scheduled visit (on natural scale). %Inhibition from baseline will be calculated as $100 * (1 - \text{fold change from baseline})$, where $\text{fold change} = \text{post baseline value} / \text{baseline value}$. Observed values that are BLQ will be set to 0 in the calculation of descriptive statistics. If sample protein concentration data are available, the activity of NE, CatG and PR3 should be normalized by the protein concentration, to generate activity values of ng/ml/mg protein, and the normalized NSP data will be presented in the same way as described above.

The neutrophil count summary will be included in the safety (hematology) analyses.

The following figures will be provided for each PD test for concentrations in blood and in sputum:

- Mean (+/- SD) over time using scheduled sampling time on natural scale by dose level overlaid in the same figure.
- Mean %inhibition (+/- SD) values over time using scheduled sampling time by dose level overlaid in the same figure.
- Individual participant profiles for PD data over time at scheduled visits – the participant's dose levels will be distinguished by different colors (spaghetti plots).

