13. CHANGES TO PROTOCOL-SPECIFIED ANALYSES

Currently, no changes from the protocol-specified analyses are planned.

A Screened Analysis Set was defined in [Section 6.1](#) in addition to the analysis sets defined in the CSP.

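### The SAP omits the protocol's within-stratum summary of NE, CatG and PR3 pooled across brensocatib doses and does not declare the omission, leaving non-modulator PD summaries on about 2 participants per dose

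*SAP*

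**What the plan says.** Protocol 9.4.4 sets two table layouts for NE, CatG and PR3 in sputum and blood. One is by treatment group, meaning each brensocatib dose and pooled placebo. The other is "by treatment group within strata (CFTR modulator and non-modulator, pooled data across all dose levels". The summary of changes for Amendment 2 gives the reason for the second: "Proposed change due to the anticipated smaller number of participants in the CFTR non-modulator stratum".

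SAP 12 refers to SAP 7.1 for the general table layout. SAP 7.1 states: "Tables and figures will be provided by treatment group/dose level". It adds: "If sample sizes permit, summaries will be further stratified by CFTR modulator and non-modulator". On what is displayed, it says: "Treatment arm/dose levels will be presented in this stratified analysis if the number of observations is" at least 2. A column combining all arms is confined to other parts of the report: "For tables in the demographic and safety sections, also a Total column will be presented". The group figures in SAP 12 are also laid out by dose, for example: "Mean %inhibition (+/- SD) values over time using scheduled sampling time by dose level overlaid in the same figure".

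SAP 13 states: "Currently, no changes from the protocol-specified analyses are planned". The one addition it records is a Screened Analysis Set. SAP 2 gives the SAP precedence wherever it differs from the protocol.

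**The concern.** The sponsor foresaw that the non-modulator stratum would be too thin to read dose by dose and wrote pooling into the protocol as the answer. The SAP carries pooling within stratum across to PK only (SAP 11.1.3, conditional on dose proportionality). Because the SAP prevails, a programmer working from it would not produce the pooled PD table, and nothing in SAP 13 would alert a reader of the study report.

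At stake is the planned summary of whether the PD response is also seen without CFTR modulators. Two features of the plan make cells of 2 especially fragile. Sputum is not required from participants who cannot produce it (Protocol 8). Geometric means and gCV use only quantifiable values above zero (SAP 7.1), so one BLQ result in a cell of 2 leaves a geometric mean from a single value and no gCV. For PK parameters, SAP 7.1 withholds descriptive statistics below three values; it sets no such floor for PD.

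**Working it through.** **1. Where a pooled PD summary could come from.**

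| Place | Pools doses within stratum for PD? |
|---|---|
| Protocol 9.4.4 | Yes, for NE, CatG and PR3 |
| SAP 7.1, layout | No; by dose, then split by stratum if numbers allow |
| SAP 7.1, Total column | No; demographic and safety tables only |
| SAP 12 | No; refers to 7.1, group figures by dose |
| SAP 11.1.3 | Pools within stratum, but for PK only |
| SAP 13 | Does not mention it |

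**2. Cell sizes (SAP Table 1 and SAP 4.1).** Non-modulator participants on active treatment: 2 per dose. Pooled over three doses: 3 × 2 = 6. With 65 mg: 4 × 2 = 8. Non-modulator placebo: about 1, or 2 with the 65 mg cohort.

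**3. Chance that a cell is shown.** Neither document gives a sputum success rate, so assume each participant has an evaluable sample at a given visit with probability q, independently. A cell of 2 reaches the threshold with probability q². A pooled group of 6 reaches it with probability 1 − (1−q)⁶ − 6q(1−q)⁵.

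| q | Cell of 2 | Pooled 6 |
|---|---|---|
| 0.9 | 0.81 | 1.00 |
| 0.8 | 0.64 | 0.998 |
| 0.7 | 0.49 | 0.989 |
| 0.5 | 0.25 | 0.89 |

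**4. Precision, as illustration.** The formula is: factor = exp( t(0.975, n−1) × √ln(1+CV²) / √n ).

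It reproduces all nine factors in SAP Tables 2 and 3 at gCV 30/40/50%: 1.234/1.317/1.402 for N=10, 1.312/1.428/1.548 for N=7 and 1.440/1.613/1.798 for N=5.

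At an assumed gCV of 40%, √ln(1.16) = 0.385:
- n=2: exp(12.706 × 0.385/√2) ≈ 31.9
- n=6: exp(2.571 × 0.385/√6) ≈ 1.50
- n=8: exp(2.365 × 0.385/√8) ≈ 1.38

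At 30% the factors are 14.0, 1.36 and 1.28. At 50% they are 69.7, 1.64 and 1.48.

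**5. Effect of mixing doses.** The pooled factors above assume that all doses share one mean. Suppose instead that each step from 10 to 25 to 40 mg halves the geometric mean (an assumption, for illustration). With 2 participants per dose, the between-dose part of the log variance is 4 × (ln 2)²/5 = 0.384. Adding 0.148 within dose gives 0.532, and the factor at n=6 becomes exp(2.571 × √0.532/√6) ≈ 2.15 rather than 1.50.

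**The case against.** The strongest reply is that the SAP's layout is itself grounded in the protocol. Protocol 9.4.1 calls for summaries by treatment group within strata if the data warrant, with treatment group meaning dose level, and 9.4.4 asks for mean plots by treatment group within each stratum. This stands: a reader might infer that by-dose output within strata contradicts the protocol, and it does not. The gap is that one of two protocol layouts is missing. The pooling phrase also sits awkwardly beside the reference to treatment group, but the amendment's rationale makes pooling across doses its natural reading.

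A reader might also infer that the trial could not describe the PD response without modulators. The documents do not support that. SAP 7.1 provides listings for all summaries and marks modulator status on them, and SAP 12 plots individual PD profiles coloured by dose. The SAP also does not commit to cells of 2: stratified summaries are conditional, so the non-modulator table may not appear at all.

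The precision figures need restraint as well. The SAP plans no confidence intervals for PD summaries, the 30 to 50% gCV range comes from PK data, and dose differences would widen the pooled interval. Pooling does little for the comparator, since non-modulator placebo is only about 1 or 2. Finally, PD is exploratory and no hypothesis is tested. These points limit the consequence but do not explain why a protocol-specified summary is absent without being declared.

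**Conclusion.** The point holds as an undeclared omission. The protocol specifies a pooled within-stratum PD summary, the SAP does not produce it, and SAP 13 reports no change. As written, non-modulator PD summaries would rest on about 2 participants per dose, or not be shown when a sample is missing, instead of about 6 pooled (8 with 65 mg). Those counts come directly from the planned allocation. The display probabilities depend on an assumed sputum success rate. The interval factors (about 32, 1.50 and 1.38 at n = 2, 6 and 8 with gCV 40%) only illustrate how little two values convey. The SAP does not say that doses must not be pooled; it simply leaves the summary out. Because the endpoints are exploratory and the individual data stay visible, the loss is a prespecified summary. It is worth correcting before database lock and does not threaten the primary objectives.

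**What to change.** In SAP 12, with a cross-reference in SAP 7.1, add within each CFTR stratum a column for all brensocatib doses pooled. It should cover observed values and percent inhibition from baseline (the SAP's PD measure) for NE, CatG and PR3, in blood and in sputum. Place pooled placebo beside it where n is at least 2, noting that without the 65 mg cohort the non-modulator placebo group will probably miss that threshold. Keep the existing by-dose tables and figures. If the pooled summary was dropped on purpose, state and justify that in SAP 13 instead.

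The cost is about one column per stratum in each PD table, with no new data. The downside is that the pooled column mixes doses whose PD effects may differ; a footnote giving the number of participants per dose, read with the retained by-dose displays, deals with that.
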